1.1. Objectives, Endpoints, and Estimands

Objectives	Endpoints
Primary	
To evaluate the efficacy of peresolimab compared to placebo in achieving ACR20	Proportion of participants achieving ACR20 at Week 12
Secondary	
To evaluate the effect of peresolimab compared to placebo for measures of disease activity To evaluate the effect of peresolimab compared to placebo for patient-reported outcome measures	 Proportion of participants achieving ACR50 or ACR70 at Week 12 Proportion of participants achieving LDA or remission at Week 12 for DAS28-hSCRP DAS28-ESR SDAI, and CDAI. Change from baseline at Week 12 for mean DAS28-hsCRP SDAI, and CDAI. Change from baseline at Week 12 for ACR core set values 68 tender joint count 66 swollen joint count, and Physician's Global Assessment of Disease Activity (VAS). Change from baseline at Week 12 for patient-reported ACR core set values Patient's Global Assessment of Disease Activity (VAS) Patient's Assessment of Arthritis Pain (VAS), and Patient's Assessment of Physical Function using HAQ-DI. Change from baseline at Week 12 for the duration and severity of morning joint stiffness and Functional Assessment of Chronic Illness Therapy-Fatigue (FACIT-F) scores. Change from baseline at Week 12 for SF-36 domains SF-36 Physical Component Summary, and
	o SF-36 Physical Component Summary, and
	 SF-36 Mental Component Summary.

Objectives	Endpoints
To evaluate the effect of peresolimab for measures of	Proportion of participants achieving LDA or
disease activity	remission at Weeks 24 and 60 for
	o DAS28-hsCRP
	o DAS28-ESR
	o SDAI, and
	o CDAI.
	 Proportion of participants achieving ACR20,
	ACR50, or ACR70 at Weeks 24 and 60.
	Change from baseline at Weeks 24 and 60 for
	ACR core set values
	o 68 tender joint count
	o 66 swollen joint count, and
	 Physician's Global Assessment of Disease
	Activity (VAS).
	• Change from baseline at Weeks 24 and 60 for mean
	o DAS28-hsCRP
	o SDAI, and
	o CDAI.
To characterize the pharmacokinetics of peresolimab	Observed trough drug concentration at Week 12
Exploratory	

Primary estimand

The primary clinical question of interest is:

What is the difference between peresolimab and placebo in the target patient population, in achieving a successful response at Week 12 without use of rescue or prohibited medications or discontinuing the study intervention?

The estimand is described by the following attributes:

- Population: Participants with moderately-to-severely active RA
- Endpoint: American College of Rheumatology (ACR) 20 at Week 12
- How to account for intercurrent events (ICEs): ICEs related to study intervention include the use of rescue or prohibited medication and early discontinuation (ED) from the study or study intervention. A composite strategy will be used for these types of ICEs. Specifically, participants with ICEs related to study intervention will be considered as treatment failure (having no change from baseline), that is, a nonresponder, after the first occurrence of these ICEs.
- Population-level summary: Difference in proportion of participants achieving response at Week 12 between each dosing regimen of peresolimab and placebo
- Rationale for estimand: The primary estimand strategy assumes that:

- o If a participant used any rescue or prohibited medication, the participant was not receiving sufficient benefits from study intervention.
- o If a participant early discontinued the study or study intervention, the participant experienced a burden of study intervention that outweighed its benefits.

Secondary estimand for categorical endpoints at Week 12

For secondary objectives that have categorical endpoints analyzed at Week 12, the clinical question of interest is:

What is the difference between peresolimab and placebo in the target patient population, in achieving a successful response at Week 12 without use of rescue or prohibited medications or discontinuing the study intervention?

The estimand is described by the following attributes:

- Population: Participants with moderately-to-severely active RA
- Endpoint(s): ACR50, ACR70, Disease Activity Score high-sensitivity C-reactive protein (DAS28-hsCRP) low disease activity (LDA), Disease Activity Score erythrocyte sedimentation rate (DAS28-ESR) LDA, Simplified Disease Activity Index (SDAI) LDA, Clinical Disease Activity Index (CDAI) LDA, DAS28-hsCRP remission, DAS28-ESR remission, SDAI remission, and CDAI remission at Week 12
- How to account for ICEs: ICEs will be accounted using the same estimand strategy as for the primary estimand.
- Population-level summary: Difference in proportion of participants achieving response at Week 12 between each dosing regimen of peresolimab and placebo
- Rationale for estimand: Refer to the rationale for the primary estimand.

Secondary estimand for continuous endpoints at Week 12

For secondary objectives that have continuous endpoints analyzed at Week 12, the clinical question of interest is:

What is the difference between peresolimab and placebo in the target patient population, in average change from baseline to Week 12 if all participants continued with treatment for 12 weeks without use of rescue or prohibited medications?

The estimand is described by the following attributes:

- Population: Participants with moderately-to-severely active RA
- Endpoint(s): Change from baseline for DAS28-hsCRP, SDAI, CDAI, 68 tender joint count (TJC68), 66 swollen joint count (SJC66), Physician's Global Assessment of Disease Activity (visual analog scale [VAS]), Patient's Global Assessment of Disease Activity (VAS), Patient's Assessment of Arthritis Pain (VAS), patient's assessment of physical function using the Health Assessment Questionnaire Disability Index (HAQDI), the duration and severity of morning joint stiffness, and Functional Assessment of Chronic Illness Therapy-Fatigue (FACIT-F) scores at Week 12

- How to account for ICEs: ICEs related to study intervention include the use of rescue or prohibited medication and ED from the study or study intervention. A hypothetical strategy will be used for these types of ICEs. Specifically, data collected after the first occurrence of ICE related to study intervention will be excluded from an analysis, and what the treatment effect would have been if rescued or prohibited medication(s) was not used, and all patients adhered to the treatment for 12 weeks will be estimated.
- Population-level summary: Difference in mean change from baseline to Week 12 between intervention conditions
- Rationale for estimand: The data collected after the treatment discontinuation, or the use of rescue or prohibited medication will not present the true efficacy effects.

Secondary estimand for categorical endpoints at Week 24 and Week 60

For secondary objectives that have categorical endpoints analyzed at Week 24 (or Week 60), the clinical question of interest is:

What is the proportion of achieving a successful response at Week 24 (or Week 60) in the target patient population without use of rescue or prohibited medications or discontinuing the study intervention?

The estimand is described by the following attributes:

- Population: Participants with moderately-to-severely active RA
- Endpoint(s): ACR20, ACR50, ACR70, DAS28-hsCRP LDA, DAS28-ESR LDA, SDAI LDA, CDAI LDA, DAS28-hsCRP remission, DAS28-ESR remission, SDAI remission, and CDAI remission at Week 24 (or Week 60)
- How to account for ICEs: ICEs will be accounted using the same estimand strategy as for the primary estimand.
- Population-level summary: Proportion of participants achieving response at Week 24 (or Week 60) in each dosing regimen of peresolimab
- Rationale for estimand: Refer to the rationale for the primary estimand.

Secondary estimand for continuous endpoints at Week 24 and Week 60

For secondary objectives that have continuous endpoints analyzed at Week 12, the clinical question of interest is:

What is the average change from baseline to Week 24 (or Week 60) in the target patient population if all participants continued with treatment for 12 weeks without use of rescue or prohibited medications?

The estimand is described by the following attributes:

- Population: Participants with moderately-to-severely active RA
- Endpoint(s): Change from baseline for DAS28-hsCRP, SDAI, CDAI, TJC68, SJC66, and Physician's Global Assessment of Disease Activity (VAS) at Week 24 (or Week 60)

- How to account for ICEs: ICEs will be accounted using the same estimand strategy as for the secondary estimand for continuous endpoint at Week 12. It will be assumed that the same level of efficacy prior to the first ICE will continue, that is, last observation carried forward (LOCF) will be used for imputation.
- Population-level summary: Mean change from baseline to Week 24 in each intervention conditions
- Rationale for estimand: Refer to the rationale for the secondary estimand for continuous endpoints at Week 12.

1.2. Study Design

Study KDAF is a Phase 2b, randomized, double-blind, placebo-controlled study to determine the appropriate dose and dosing frequency of peresolimab in adult participants with moderately-to-severely active RA.

[figure not shown]
This study includes a

- Period 1: screening period occurring approximately 1 to 42 days prior to Period 2
- Period 2: 12-week double-blind, placebo-controlled treatment period
- Period 3: 48-week double-blind treatment period, and
- Period 4: posttreatment follow-up period occurring 4 and 12 weeks from last treatment period visit (Week 60) or Early Discontinuation Visit.

See the Schedule of Activities (SoA) in the protocol for visit schedule, procedural and assessment details.

In the remainder of this statistical analysis plan (SAP), the first 12 weeks in Period 3 (that is, Weeks 12 to 24) will be referred as Period 3A and the last 36 weeks in Period 3 (that is, Weeks 24 to 60) as Period 3B for an analysis purpose. Combined Periods 2 and 3 will be referred as the Treatment Period (Weeks 0 to 60).

Figure KDAF.1.1 describes the study design for the treatment periods (Periods 2 and 3).

[figure not shown]

Abbreviations: CDAI = Clinical Disease Activity Index; SC = subcutaneous injection; Q4W = every 4 weeks; Q12W = every 12 weeks.

Note: At Week 12, participants receiving placebo Q4W will begin receiving either 400 mg or 1000 mg peresolimab Q4W. At Week 24, participants receiving 400 mg or 1000 mg peresolimab Q4W may be switched to Q12W dosing following assessment of CDAI scores.

Figure KDAF.1.1 Study design.

Participant population

Treatment period design

- 100 mg of peresolimab every 4 weeks (Q4W)
- 400 mg of peresolimab Q4W
- 1000 mg of peresolimab Q4W
- placebo Q4W up to Week 12 followed by 400 mg of peresolimab Q4W, and
- placebo Q4W up to Week 12 followed by 1000 mg of peresolimab Q4W.

Participants randomly assigned to placebo Q4W at Week 0

At Week 12, participants receiving placebo Q4W will begin receiving either 400 mg or 1000 mg peresolimab Q4W based on randomization at Week 0. Treatment assignment will be blinded, and the participants will continue their assigned peresolimab dose and dosing frequency until the end of the study.

Participants randomly assigned to 100 mg peresolimab at Week 0

Participants receiving 100 mg peresolimab will continue their assigned dose and dosing frequency throughout the duration of the treatment period. No changes will occur.

Participants randomly assigned to 400 mg or 1000 mg peresolimab at Week 0

Participants receiving 400 mg or 1000 mg peresolimab will continue their assigned dose and dosing frequency until Week 24. At Week 24, participants may be switched to every 12 weeks (Q12W) dosing following assessment of CDAI scores, unless they received rescue medication prior to Week 24.

Abbreviations: CDAI = Clinical Disease Activity Index; Q4W = every 4 weeks; Q12W = every 12 weeks.

- At Week 24 using the Visit 9 (Week 24) assessments, a participant does not achieve CDAI LDA
 - o These participants will receive permitted rescue therapy.
- For participants that achieved CDAI LDA at Week 24, those who do not maintain CDAI LDA for 2 consecutive visits after Week 24
 - o These participants will receive peresolimab Q4W and permitted rescue therapy.
 - If a participant is currently receiving peresolimab Q4W, they will continue receiving peresolimab Q4W.

• If a participant is currently receiving peresolimab Q12W, they will switch to peresolimab O4W.

[figure not shown]
Escape criteria after Week 24

A participant not achieving ≥20% improvement in both TJC and SJC at 2 consecutive visits after Week 24, while receiving rescue therapy, should be permanently discontinued from study intervention. Participants may continue in the study and receive additional standard of care therapies at the investigator's discretion.

Participation in an open-label extension study

If an open-label extension study is enrolling at the time the participant completes Visit 18 (Week 60), they will be given the opportunity to enroll in that study.

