Data collected after initiation of rescue or prohibited medication use will be handled according to the specified estimand strategy for efficacy analysis. Such data, unless otherwise noted, will be excluded from efficacy analyses, considered as missing, and handled according to a missing data imputation method as specified.

Missing data will be handled separately from estimand strategy. After intercurrent events related to study intervention are accounted for according to an estimand strategy specified in Section 1.1, any remaining missing data will be handled using the following missing data imputation methods:

• Nonresponder imputation (NRI):

When NRI is applied, participants with missing data will be considered as nonresponders regardless of whether they have at least 1 postbaseline data.

• LOCF:

When LOCF is applied, the last nonmissing observation up to Week 24 will be carried to the corresponding time point for evaluation. For participants who initiated rescue therapy, the last nonmissing observation prior to the initiation of rescue therapy will be carried forward. For randomized participants without any postbaseline observation, missing data will not be imputed.

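### Mandatory rescue at Week 24 combined with the composite and carry-forward rules fixes the Week 60 results of the Maintenance Secondary Population at Week 24, so a supplementary summary regardless of rescue is needed

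*SAP*

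**What the plan says.** **Rescue rule (SAP 1.2).** The Week 24 trigger reads: "At Week 24 using the Visit 9 (Week 24) assessments, a participant does not achieve CDAI LDA". The consequence is stated as something that happens, not as an option: "These participants will receive permitted rescue therapy". A second trigger covers Week 24 LDA achievers, namely "those who do not maintain CDAI LDA for 2 consecutive visits after Week 24"; they also receive rescue.

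**Intercurrent events (SAP 1.1).** "ICEs related to study intervention include the use of rescue or prohibited medication and early discontinuation (ED) from the study or study intervention". Under the composite strategy the participant becomes "a nonresponder, after the first occurrence of these ICEs", with no point at which that status ends. For the Week 24 and Week 60 categorical endpoints: "ICEs will be accounted using the same estimand strategy as for the primary estimand". SAP 4.4.3.2 and Table KDAF.4.2 repeat the composite strategy with nonresponder imputation for Week 60 in the Maintenance Primary, Secondary and Tertiary Populations.

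**Continuous endpoints.** SAP 1.1 assumes that the level of efficacy before the first event continues, using LOCF. SAP 4.1 adds that for rescued participants "the last nonmissing observation prior to the initiation of rescue therapy will be carried forward".

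**Populations.** SAP 1.2.1 re-randomises 400 mg and 1000 mg participants with CDAI of 10 or less at Week 24 to Q4W or Q12W, and SAP 1.2 bars the Q12W switch after earlier rescue. Table KDAF.3.1 shows 400 mg and 1000 mg, each Q4W and Q12W, in the Primary Population. It shows 400 mg Q4W and 1000 mg Q4W only in the Secondary, and the 100 mg and placebo-switch groups in the Tertiary.

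**The concern.** The rescue trigger is a disease-activity target, whereas most of the Week 60 endpoints measure something else. A participant whose CDAI falls from 40 to 15 with a sustained ACR50 response misses LDA, is rescued at Week 24, and is then an ACR20 failure at Week 60 even if the response never wavers.

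Where a whole analysis population is made up of such participants, its Week 60 result is known before any Week 60 assessment takes place. Week 60 disease activity is a declared secondary objective in a study meant to settle dose and dosing frequency. The 400 mg and 1000 mg arms would appear at Week 60 as one group selected for LDA and one group at about 0%. The 100 mg arm appears only in the Tertiary Population. A reader could mistake that pattern for loss of effect after Week 24 or for a dose pattern.

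**Working it through.** **Inputs from the documents.** SAP Section 5 gives Week 12 group sizes of 60 (100 mg), 120 (400 mg), 120 (1000 mg) and 120 (placebo). Their sum, 60 + 120 + 120 + 120 = 420, reproduces the stated total. CDAI LDA is a score of 10 or less (Table KDAF.4.1), the same cut-off as for re-randomisation. The Week 60 categorical estimand lists 11 endpoints: 3 ACR levels, plus LDA and remission on each of 4 indices (3 + 4 + 4 = 11). The continuous estimand lists 6.

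**Inputs assumed.** The documents show no Week 24 LDA rate and no expected Week 60 rate.
- L, the Week 24 CDAI LDA rate: 10% to 50%.
- q, the share of participants outside LDA who actually take rescue: 100% if the rule is followed.
- m, the share of Week 24 LDA achievers rescued later.

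**Step 1: who is in the Secondary Population.** A 400 mg or 1000 mg participant who is not re-randomised is either outside LDA at Week 24, and so rescued by rule, or already rescued. Both routes give an intercurrent event by Week 24.

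**Step 2: upper bounds on composite response at Week 60.** A responder must have no intercurrent event by then, so:
- Secondary ≤ 1 − q
- Tertiary ≤ L(1 − m) + (1 − L)(1 − q), if the Week 24 rule applies to those arms
- Primary ≤ 1 − m

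With q = 1 the Secondary bound is 0 for all 11 endpoints. The Tertiary bound is L(1 − m), which is at most L; with L = 30% and m = 20% it is 0.30 × 0.80 = 24%. The Primary bound does not involve L, because everyone enters that population in LDA.

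**Step 3: continuous endpoints.** With q = 1, every Secondary participant's Week 60 value is the last value before rescue, taken at Week 24 or earlier. The Week 60 mean therefore contains no Week 60 information.

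**Step 4: size.** The second column is 120(1 − L), ignoring dropout and earlier rescue. The last two columns illustrate a Tertiary arm with assumed Week 60 ACR20 of 90% in Week 24 LDA achievers and 40% in the rest, q = 1 and m = 0. The composite rate is then 0.90L, and the rate regardless of rescue is 0.90L + 0.40(1 − L).

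| Assumed L | Secondary, of 120 per arm | Tertiary ceiling | Composite ACR20 | ACR20 regardless of rescue |
|---|---|---|---|---|
| 10% | 108 | 10% | 9% | 45% |
| 20% | 96 | 20% | 18% | 50% |
| 30% | 84 | 30% | 27% | 55% |
| 40% | 72 | 40% | 36% | 60% |
| 50% | 60 | 50% | 45% | 65% |

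**Step 5: incomplete rescue uptake.** If 5% or 10% of participants outside LDA take no rescue, and 40% of them respond, the Secondary rate is 0.05 × 0.40 = 2% or 0.10 × 0.40 = 4%. The Tertiary ceiling at L = 30% becomes 0.30 + 0.70 × 0.05 = 33.5%, or 0.30 + 0.70 × 0.10 = 37%.

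**The case against.** The best defence is that this is a declared estimand. The Week 60 question asks for response without rescue, and the absence of unrescued responders among rescued participants answers it correctly. The protocol introduction names sustained LDA or remission as the treatment target, so missing LDA can reasonably count as insufficient benefit. That stands, and it is why the composite analysis need not be withdrawn. It does not make the resulting table informative about Week 60.

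Several stronger readings are tempting, but the documents do not support them:
- *The Secondary result is exactly 0%.* The event is use of rescue, not meeting the trigger, so incomplete uptake leaves a small non-zero rate. Membership is also inferred from SAP 1.2, 1.2.1 and Table KDAF.3.1, because the set definitions in Section 3 are not readable.
- *Week 60 rates in all other groups are capped by Week 24 LDA.* The cap does not bind in the Primary Population. For the Tertiary arms it is likely but unconfirmed: the rescue bullets are worded generally, but they follow a heading for the 400 mg and 1000 mg arms and their lead-in is not readable.
- *The plan has no summary regardless of rescue.* Parts of the estimand and analysis text are not readable, so this cannot be asserted. No such summary appears in the readable text.
- *A trial conclusion is biased.* The Week 60 results are descriptive, with no comparison between treatments. The Week 12 primary analysis is untouched, and rescue started on the Week 24 assessment does not affect Week 24 response.

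Replacing the main analysis in only the Secondary and Tertiary Populations would put regimens on different scales at Week 60, so an addition on one common basis is preferable.

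**Conclusion.** The concern holds, at the level of an improvement that should be made. If the Week 24 rescue rule is followed, Week 60 results in the Maintenance Secondary Population are settled by Week 24: about 0% on all 11 binary endpoints (2% to 4% in the illustration with 5% to 10% non-uptake), and pre-rescue values on the 6 continuous endpoints. In the Maintenance Tertiary Population, Week 60 response is bounded by the Week 24 LDA rate apart from rescue non-uptake, provided the rule applies to those arms.

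The conclusion rests on the inferred membership of the Secondary Population and on near-complete rescue uptake. The head counts and the 90%/40% illustration rest on assumed rates. The harm is to interpretation: descriptive secondary tables that say nothing about Week 60 and could be read as loss of effect.

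**What to change.** Keep the composite and hypothetical analyses as declared. Add to SAP 1.1, SAP 4.4.3.2 and Table KDAF.4.2 a prespecified supplementary summary for Period 3B visits including Week 60, on the same basis in the Maintenance Primary, Secondary and Tertiary Populations:

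- Use observed values regardless of permitted rescue, labelled *peresolimab with or without permitted rescue*.
- For binary endpoints, apply nonresponder imputation only for missing data or discontinuation.
- For continuous endpoints, do not carry pre-rescue values forward.
- Show the number and percentage rescued beside every result.

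If unreadable parts of the SAP already contain such a summary, a cross-reference from these three places is enough. The cost is SAP wording and one extra set of tables. Joint counts at least must continue under rescue, because the escape rule in SAP 1.2 relies on them. The drawback is that the added summary describes drug plus rescue, which the label states. The clinical rescue rule is not changed.

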1.2.1. Method of Assignment to Treatment

- 100 mg of peresolimab Q4W
- 400 mg of peresolimab Q4W
- 1000 mg of peresolimab Q4W
- placebo Q4W up to Week 12 followed by 400 mg of peresolimab Q4W, and
- placebo Q4W up to Week 12 followed by 1000 mg of peresolimab Q4W.

Participants who are randomized to either peresolimab 400 mg Q4W or peresolimab 1000 mg Q4W at Week 0 and meet CDAI \leq 10 at Week 24 will be randomly assigned to either Q4W or Q12W in the same dose level with a 1:1 ratio. Participants will be stratified by

• CDAI <2.8 vs 2.8 < CDAI <6 vs CDAI >6 at Week 24.

2. Statistical Hypotheses

The primary objective is to demonstrate that peresolimab is superior to placebo in achieving ACR20 at Week 12. Thus, the null hypothesis to be tested in relation to the primary estimand is:

There is no difference between peresolimab and placebo when evaluating the proportion of study participants with moderately-to-severely active RA achieving ACR20 at Week 12.

